5.4 Baseline Visit (within 10 days from enrollment)

The following information will be collected at the baseline visit

- Demographics- include subject's year of birth and gender
- Physical examination- include subject's height, weight, blood pressure (measurements taken during visit)
- Arrhythmia history
 - o The types and classification of atrial fibrillation (AF) and atrial tachycardia (AT) are determined in reference to the 2012 HRS/EHRA/ECAS Expert Consensus Statement on Catheter Ablation of Atrial Fibrillation

Clinical Investigational Plan

- The types and classification of ventricular arrhythmias are determined in reference to the 2009 EHRA/HRS Expert Consensus on Catheter Ablation of Ventricular Arrhythmias
 - Cardiac history (most recent values closest to baseline visit)
 - Indication for procedure - specify type of arrhythmia and information on previous treatments
 - Medical history - indicate subject's relevant co-morbidities, previous cardiac procedures
 - 12-Lead ECG measurement (most recent ECG available, max. 2 months old)
 - Antiarrhythmic medication - indicate both the medication that failed and the medication (if any) the patient is currently taking
 - Anticoagulant medication – medication the patient is currently taking
 - Any deviation that might have occurred

5.5 Procedure Visit (within 14 days from Baseline visit)

The procedure should be performed according to the instructions for use (IFU) of the EnSite Precision™ Cardiac Mapping System, the IFU of AutoMark feature and AutoMap™ and other medical devices used during the procedure.

Subjects will be prepared according to the standard surgical procedures and standard practice of the center. The procedure should always be done with the aid of fluoroscopy.

Instances where fluoroscopy images should be collected and uploaded via Electronic Data Capture (EDC):

- At procedure start, after initial catheters are in place. Consider placing catheters in reproducible locations within the chamber of interest.
- At procedure end, prior to removal of catheters. Replicate catheter location(s) used previously.
- At any point during the procedure where an instance of instability might have occurred. Replicate catheter location(s) used previously.

The anonymized images should be uploaded using following naming convention:

- SiteID_PatientID_Fluoro Procedure Start
- SiteID_PatientID_Fluoro Procedure End
- SiteID_PatientID_Fluoro Procedure Instance of Instability

(in case of multiple possible instances, please number them accordingly)

Please refer to the Procedure Guidelines (provided in a separate document) for more detailed information.

Concerning additional data collection, please refer to the procedure guidelines. These guidelines are not mandatory, however, they may assist in current knowledge and understanding of the treatment options for patients with arrhythmias.

The entire study (EPS) should be backed up on a USB drive (provided by sponsor) and returned to the sponsor within reasonable timelines. Please refer to the Procedure Guidelines for additional information.

The User Experience Form should be completed once by every physician performing a procedure for this registry.

Clinical Investigational Plan

NOTE: The EnSite Precision™ System interfaces to either the MediGuide™ Guided Medical Positioning System or the EnSite Precision™ Module to combine and display magnetic processed patient positioning and orientation mapping information. In order to use these features, the Electrophysiologist (EP) will need to use at least one sensor enabled (SE) catheter (e.g, Advisor™ FL Circular Mapping Catheter, Sensor Enabled™ or FlexAbility™ SE Ablation Catheter) in the area or chamber of interest. Physicians or hospitals that wish to use the system without an SE catheter may do so, however the use of an SE catheter is strongly encouraged in order to take full advantage of system features.

NOTE: The EnSite™ AutoMap™ Module is a software entitlement feature within the EnSite Cardiac Mapping System. AutoMap automates the point collection process, based on the user-defined settings. As the catheter is moved, points are collected when the user-defined settings are met.

NOTE: The AutoMark feature provides the capability to visualize ablation parameter data and contact force data at the catheter tip on the EnSite Precision™ Cardiac Mapping System display. The EP can configure the software to display generator data including time, duration, power temperature and catheter dwell time.

NOTE: Any adverse event (refer to section 7.0 for details) and/or protocol deviations (refer to section 6.2 for details) at the procedure will also be recorded at this time.

5.6 Pre-Discharge (within 7 days post Procedure)

The pre-discharge visit needs to be performed within 7 days post procedure.

The activities and data collected at pre-discharge include the following:

- Physical examination – Blood pressure
- 12-lead ECG measurement
- Medication – indicate any changes in anticoagulant medication
- Any reportable adverse event that might have occurred since the procedure
- Any deviation that might have occurred

5.7 Description of Activities performed by Sponsor Representatives

Trained sponsor personnel may perform certain activities to ensure compliance to the clinical investigational plan and may provide technical expertise.

Sponsor personnel will not:

- Administer the informed consent process
- Practice medicine
- Provide medical diagnosis or treatment to subjects
- Discuss a subject's condition or treatment with a subject without the approval and presence of a health care practitioner
- Independently collect registry data

5.8 Subject Registry Completion

When the subject's participation in the registry has been completed, i.e. after the pre-discharge visit, the subject will return to medical care as per physician's recommendation.

Clinical Investigational Plan

5.9 Any known or foreseeable Factors that may compromise the Outcome of the Registry or the Interpretation of the Results

All foreseeable factors that may compromise the outcome have been taken into account

- Recruitment plans
- Enrollment of an insufficient variety of arrhythmias which might result in a prolonged and extended enrollment period
- Enrollment targets

5.10 Description of the Methods that will be used to address potentially confounding Factors in the Design

Methods used to address potentially confounding factors are:

- Ensure a variety of EP cases by introducing a screening tool that will facilitate patient inclusion based on arrhythmia history.

5.11 Criteria and Procedures for Subject Withdrawal or Discontinuation

Subjects must be informed about their right to withdraw from the registry at any time and for any reason without sanction, penalty or loss of benefits to which the subject is otherwise entitled and withdrawal from the registry will not jeopardize their future medical care or relationship with the investigator. Subjects will be asked to specify the reason for the Withdrawal, but have the right not to answer.

The investigator may decide to withdraw a subject from the registry at any time with reasonable rationale. The subject's future care will not be influenced by a decision, voluntary or otherwise, to withdraw from the registry. All reasonable efforts should be made to retain the subject in the registry until completion of the registry.

Any withdrawal prior to the procedure (for any reason), should only be documented on a Withdrawal Form.

Reasons for subject's withdrawal include, but are not limited to:

- Subject refuses to continue participation in the registry
- Subject is deceased (cause must be documented)
- Subject's non-compliance
- Subject is 'lost to follow up': Subject does not adhere to the scheduled follow up visits but has not explicitly requested to be withdrawn from the registry. (This does not apply to missed visits). Site personnel should at all times make all reasonable efforts to locate and communicate with the subject in order to achieve subject compliance to the scheduled follow up visits:
 1. A subject will be considered 'Lost to Follow Up' after a minimum of 2 phone calls of a physician or delegate at the site to the subject or contact. These 2 phone calls need to be documented in the subject's hospital records.
 2. If these attempts are unsuccessful, a letter should be sent to the subject's last known address or general practitioner (GP) and a copy of this letter should be maintained in the subject's hospital records.

If a subject withdraws from the registry, the site will record the subject's reasons for withdrawal, on a Withdrawal Case Report Form (CRF).

Clinical Investigational Plan

6.0 COMPLIANCE TO CIP

6.1 Statement of Compliance

The registry will be performed in accordance with the most current versions of the World Medical Association (WMA) Declaration of Helsinki, ISO14155 and any regional and/or national regulations and will be compliant to this International Standard and any regional and national regulations, as appropriate.

The investigator will not start enrolling subjects or requesting informed consent from any subject prior to obtaining EC/IRB approval, if applicable, and authorization from the sponsor in writing for the registry.

In the case that additional requirements are imposed by the EC/IRB, those requirements will be followed, if appropriate. If any action is taken by an EC/IRB, and regulatory requirements with respect to the registry, that information will be forwarded to St. Jude Medical.

As sponsor, St. Jude Medical has taken up general liability insurance in accordance with the requirements of the applicable local laws. Appropriate country representatives will be utilized to understand the requirements for the type of insurance that will be provided for subjects, such information will be incorporated into the informed consent, as applicable

If required, additional subject coverage or a registry specific insurance will be provided by the Sponsor as well.

6.2 Adherence to the Clinical Investigational Plan

A deviation is defined as an event where the clinical investigator, site personnel, sponsor or sponsor representative did not conduct the registry according to the Clinical Investigational Plan, EC/IRB requirements or the Investigator Agreement. The investigator is not allowed to deviate from the CIP, except as specified under emergency circumstances.

In some cases, failure to comply with the CIP may be considered failure to protect the rights, safety and well-being of subjects, since the non-compliance exposes subjects to unreasonable risks. For example, failure to adhere to the inclusion/exclusion criteria: these criteria are specifically defined by the Sponsor to exclude subjects for whom the device is not beneficial and the use involves unreasonable risks. This may be considered failure to protect the rights, safety and well-being of the enrolled subject. Similarly, failure to perform safety assessments intended to detect adverse events may be considered failure to protect the rights, safety and well-being of the enrolled subject. Investigators should seek minimization of such risks by adhering to the CIP.

Simultaneously, in the event that adhering to the CIP might expose the subject to unreasonable risks, the investigator is also required to protect the rights, safety and well-being of the subject by intentionally deviating from the requirements of the CIP, so that subjects are not exposed to unreasonable risks.

It is the responsibility of the investigator to provide adequate medical care to a subject enrolled in a registry.

Regulations require that the PI maintain accurate, complete, and current records, including documents showing the date of and reason for every deviation from the Clinical Investigational Plan. Relevant information for each deviation will be documented on a Deviation Case Report Form. The site will submit the CRF to St. Jude Medical.

Clinical Investigational Plan

Regulations require Investigators obtain approval from St. Jude Medical and the EC/IRB (as required) before initiating changes in or deviations from the protocol, except when necessary to protect the life or physical well-being of a subject in an emergency. Under emergency circumstances, deviations from the CIP to protect the rights, safety and well-being of human subjects may proceed without prior approval of the sponsor and the EC/IRB. Such deviations shall be documented and reported to the sponsor and the ECIRB as soon as possible, but no later than 5 working days.

Prior approval must be requested when the PI anticipates, contemplates, or makes a conscious decision to depart from the CIP, except when unforeseen circumstances are beyond the investigator's control (e.g. a subject who fails to attend a scheduled follow-up visit, a subject is too ill to perform a CIP-required test, etc.). All deviations, including those beyond the investigator's control, must be reported on a CRF.

To obtain approval, the Principal Investigator may call or email and discuss the potential deviation with St. Jude Medical or designee prior to initiating any changes.

All deviations must be reported to appropriate regulatory authorities in specified timelines (if appropriate).

Investigators or the designee must notify St. Jude Medical, Inc. as soon as possible and complete the Deviation CRF.

The Investigator is required to adhere to local regulatory requirements for reporting deviations to EC/IRB.

6.3 Repeated and serious Non-Compliance

In the event of repeated non-compliance or a one-time serious non-compliance, as determined by the Sponsor, a Clinical Research Associate or clinical representative will attempt to secure compliance by one or more of the following actions:

- Visiting the investigator
- Contacting the investigator by telephone
- Contacting the investigator in writing
- Retraining of the investigator

If an investigator is found to be repeatedly non-compliant with the signed agreement, the CIP or any other conditions of the registry, the Sponsor will either secure compliance or, at its sole discretion, terminate the investigator's participation in the registry.

7.0 ADVERSE EVENT, ADVERSE DEVICE EFFECT

7.1 Definitions

7.1.1 Medical device

Any instrument, apparatus, implement, machine, appliance, implant, software, material or other similar or related article

- Intended by the manufacturer to be used, alone or in combination, for human beings for one or more of the specific purpose(s) of
 - Diagnosis, prevention, monitoring, treatments or alleviation of disease,
 - Diagnosis, monitoring, treatment, alleviation of, or compensation for, an injury,

Clinical Investigational Plan

- Investigation, replacement, modification, or support of the anatomy or of a physiological process,
- Supporting or sustaining life,
- Control of conception,
- Disinfection of medical devices and
- Which does not achieve its primary intended action in or on the human body by pharmacological, immunological or metabolic means, but which may be assisted in its intended function by such means

7.1.2 Adverse Event (AE)

Any untoward medical occurrence, unintended disease or injury, or untoward clinical signs (including abnormal laboratory findings) in subjects, users or other persons, whether or not related to the investigational medical device under study.

This definition includes events related to the investigational medical device or the comparator.
This definition includes events related to the procedures involved.

7.1.3 Serious Adverse Event (SAE)

An adverse event that led to:

- Death
- A serious deterioration in the health of the subject, that either resulted in:
 - A life-threatening illness or injury OR
 - A permanent impairment to a body structure or a body function OR
 - An in-patient or prolonged hospitalization OR
 - A medical or surgical intervention to prevent life-threatening illness or injury or permanent impairment to a body structure or a body OR
 - A malignant tumor
- Fetal distress, fetal death or a congenital abnormality or birth defect

A planned hospitalization for a pre-existing condition, or a procedure required by the CIP is not considered a serious adverse event.

7.1.4 Adverse Device Effect (ADE)

An adverse event related to the use of an investigational medical device.

This definition includes adverse events resulting from insufficient or inadequate instructions for use, deployment, implantation, installation, or operation, or any malfunction of the investigational medical device.

This definition includes any event resulting from the use error or from intentional misuse of the investigational medical device.

7.1.5 Serious Adverse Device Effect (SADE)

Adverse device effect that has resulted in any of the consequences characteristic of a serious adverse event.

7.2 Procedure for Assessing, Recording and Reporting Adverse Events, Complaints, Adverse Device Effects, Serious Adverse Events and Serious Adverse Device Effects

Clinical Investigational Plan

Safety surveillance within this registry and the safety reporting, both performed by the investigator, starts at the Procedure Visit and will continue until the last visit has been performed, the subject is deceased, the subject/investigator concludes his participation into the registry or the subject/investigator withdraws the subject from the registry, except as otherwise specified in the CIP.

For the purpose of this registry, all Serious Adverse Events (regardless of relatedness) and all Adverse Device Effects (regardless of severity) will be documented and reported via an eCRF to the sponsor immediately but no later than 72 hours after becoming aware of the event.

All complaints for SJM products must be reported to SJM Post Market Surveillance. The investigator should notify their SJM representative or SJM Postmarket Surveillance Department as soon as possible after becoming aware of a complaint by email to [contact] or calling [name].

Device related and/or procedure related events/complaints will be further assessed by SJM within SJM Postmarket Surveillance system.

Records relating to the subject's subsequent medical course must be maintained and submitted (as applicable) to the Sponsor until the event has subsided or, in case of permanent impairment, until the event stabilizes and the overall clinical outcome has been ascertained. Adverse events will be monitored until they are adequately resolved. The status of the subject's condition should be documented at each visit.

Subjects will be carefully monitored during the registry for possible required AEs. Any reportable AE will be followed to a satisfactory resolution, until it becomes stable, or until it can be explained by another known cause(s) (i.e., concurrent condition or medication) and clinical judgment indicates that further evaluation is not warranted. All findings relevant to the final outcome of an AE must be reported in the patient's medical record.

The clinical investigator will attempt to assess the involvement of the procedure and device in the AE. All observations and clinical findings, including the nature, severity, and relationship, will be documented on the appropriate eCRFs.

Adverse events will be assessed by the investigator for relationship to the device and to the procedures involved.

- **Procedure related:** The AE is deemed related to the procedure if it occurred during the procedure but was not directly caused by the medical device.
- **Device related:** The AE is deemed device related if it was directly caused by the medical device

The Sponsor will ensure that all events are reported to the relevant authorities as per regulations.

The investigator must notify the EC/IRB, if appropriate, in accordance with national and local laws and regulations, of the AEs reported to the Sponsor.

Additional information may be requested, when required, by the Sponsor in order to support the reporting of AEs to regulatory authorities.

Clinical Investigational Plan

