4.0 DEVICES USED

4.1 Device Description

SJM, sponsor of this registry, will ensure that the registry will only start after full CE certification of the EnSite Precision™ System has been obtained, and copies of the CE-certificates and final Instructions for Use have been sent to the relevant ECs/IRBs if required by local regulations.

Table 1: Description of Proposed Devices

Device Component	Model/Type/Version/Reference	Regulatory status
EnSite Precision™ Software	V2.0 H702496	CE Marked
EnSite Precision™ Module, Sensor Enabled	H702473	CE Marked
EnSite Precision™ Surface Electrode Kit	EN0020-P	CE Marked
AutoMap™ Module	V1.0 H702499	CE Marked
AutoMark feature	V1.0	CE Marked
Advisor™ FL Circular Mapping Catheter, Sensor Enabled™	D-AVSE-D10-F20	CE Marked
	D-AVSE-DF10-F20	
	D-AVSE-D10-F15,	
	D-AVSE-DF10-F15	
FlexAbility™ SE Ablation Catheter	A-FASE-D	CE Marked
	A-FASE-F	
	A-FASE-J	
	A-FASE-DD	
	A-FASE-FF	
	A-FASE-JJ	
	A-FASE-DF	
A-FASE-FJ		

Descriptions and Instructions for Use are available separately.

Additional tools that may be used in this registry (per physician’s discretion), include, but are not limited to:

Clinical Investigational Plan

- Tacticath™ Ablation Catheter
- FlexAbility™ Ablation Catheter
- MediGuide™ Platform
- Other commercially available catheters to facilitate EP procedures

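### Section 7.2 sets device relatedness more narrowly than the plan's own adverse device effect definition, and procedure relatedness by timing with no causal test

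*Combined protocol and SAP*

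**What the plan says.** Section 7.2 of the protocol asks for two judgements on each event: "Adverse events will be assessed by the investigator for relationship to the device and to the procedures involved". Two rules follow.

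- Procedure: "The AE is deemed related to the procedure if it occurred during the procedure but was not directly caused by the medical device".
- Device: "The AE is deemed device related if it was directly caused by the medical device".

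The definitions in 7.1 use different terms. Section 7.1.4 defines an ADE as "An adverse event related to the use of an investigational medical device". It then names events that arise from poor instructions or from malfunction, and adds: "This definition includes any event resulting from the use error or from intentional misuse of the investigational medical device". Section 7.1.2, on what counts as an adverse event, says: "This definition includes events related to the procedures involved".

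Three other provisions matter.

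- Section 7.2 makes all serious adverse events reportable whatever their relatedness, and all ADEs whatever their severity.
- Section 7.2 sends events that are device related, procedure related or both (joined by *and/or*) for further assessment in the sponsor's postmarket system. Complaints about the sponsor's products have their own route there.
- Section 5.6 collects reportable events that arose after the procedure, at a pre-discharge visit up to 7 days later.

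**The concern.** Relatedness is a causal judgement. Neither rule in 7.2 handles it in line with the rest of the plan: one replaces the causal question with a question of timing, and the other sets a stricter causal standard than the ADE definition that the same investigator must apply to the same event.

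The second gap matters for this product because a mapping system mainly informs the operator. Section 7.2.1 anticipates map shifts without warning and incorrect catheter display. If a wrong display led the operator to injure tissue, one could argue that the system did not directly cause the injury, although 7.1.4 covers any malfunction. The 7.2 wording is weakest on that indirect route.

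The synopsis (Data Collection) says that performance is assessed partly through adverse events, and section 9.0 allows the data to support a market-approval application. Section 15.0 sets up no committee and the plan describes no adjudication, so the investigator's label is the attribution on record.

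**Working it through.** No figure in the plan bears on this and no arithmetic applies. The check is to set the rules side by side and apply them to kinds of event that the plan provides for.

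**Step 1. The tests.**

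| Provision | Causal link required | Limit on timing |
|---|---|---|
| 7.1.4, ADE | Related to use of the device, including malfunction, poor instructions, use error and misuse | None |
| 7.2, device related | Direct causation by the device | None |
| 7.2, procedure related | None to the procedure; direct device causation must be absent | During the procedure |

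**Step 2. A use error during the procedure, with harm not directly caused by the device.** Under 7.1.4 this is an ADE. Under 7.2 it fails the device rule and meets both parts of the procedure rule, so it is recorded as procedure related. It still goes to postmarket assessment, but under the wrong attribution.

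**Step 3. A serious coincidental event during the procedure.** It meets the procedure rule because of when it happened. No causal link is asked for, so it is recorded as procedure related and goes to postmarket assessment.

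**Step 4. A serious procedural complication that begins after the procedure and before the pre-discharge visit.** Section 7.2.1 anticipates infection and pseudo-aneurysm, for example. If the device did not directly cause it, neither rule is met. If the rules are read as complete, it gets no label. It is still reported as a serious event, but it falls outside the class sent for postmarket assessment unless someone also files a product complaint.

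**Step 5. An event due to both device and procedure.** One rule requires direct causation by the device and the other requires its absence. If the rules are read as complete, no event satisfies both, although 7.2 itself asks for both relationships and uses *and/or*.

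**Step 6. Knock-on to reporting.** A serious event is reportable on either test. A non-serious event is reportable only if it is an ADE. An investigator who takes the 7.2 device rule as the working test for an ADE could therefore leave out a non-serious event that 7.1.4 includes.

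Steps 2 and 3 follow from the procedure rule as it stands. Steps 4 and 5 need the further reading that the rules are complete. Step 6 needs an investigator to use the narrower test when identifying ADEs.

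**The case against.** The strongest reply has four parts.

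*The rules may be sufficient, not exhaustive.* Each says *if*, not *only if*. On that reading a late complication or a double label is not barred, and *and/or* may describe a pool of events, not a single one. This stands, and it is why steps 4 and 5 are conditional. It does not rescue steps 2 and 3: meeting a sufficient condition is enough for the procedure label, and the device rule gives no basis for labelling an indirect device effect.

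*Section 7.2 first asks for a general judgement.* Just before the rules, the investigator is told to assess how far procedure and device were involved, with no limit on timing. But the rules that follow say how that relationship is deemed, so they govern what is recorded.

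*The form may be better than the text.* Appendix G keeps the case report forms under separate cover. This stands: actual misclassification cannot be shown, only what the written rules would produce.

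*The consequence is small.* All serious events reach the sponsor, adverse events are not a listed endpoint, and section 12 plans no analysis by relatedness. This stands and limits the weight of the point.

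Two stronger readings should be resisted. A reader might infer that 7.2 contradicts 7.1.2. It does not: 7.1.2 says what counts as an adverse event and gives no test of relatedness. A reader might also infer a mismatch in device scope, because 7.1.1 opens its definition of a medical device with "Any instrument, apparatus, implement, machine, appliance, implant, software, material or other similar or related article" and section 4.1 permits "Other commercially available catheters to facilitate EP procedures", while 7.1.4 speaks of the investigational device. In context, the device in 7.2 can simply mean the device under study, so that inference is speculative.

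**Conclusion.** The point holds. The device rule in 7.2 is narrower than the ADE definition in 7.1.4, and the procedure rule has no causal test. Applied as written, they would record some ADEs and some coincidental events as procedure related. If the rules are taken as complete, late procedural complications would have no label and no event could have two.

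The effect is on the recorded relatedness of reported events and on which of them go to postmarket assessment, with a possible loss of some non-serious ADEs. How many events are affected cannot be estimated: the documents give no event rates and no breakdown by cause or onset.

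A reader might go further and infer that serious events are lost or that the registry's results are biased. The documents do not support this. Serious events are reported whatever their relatedness, and no endpoint, hypothesis test or sample-size figure uses the labels. Nor is there a basis for a claim about USADE status, which 16.1 lists as a ground for termination: neither 7.1.4 nor 7.1.5 defines that term.

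This is a wording fault that should be corrected, not one that threatens the registry.

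**What to change.** In section 7.2:

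1. Align the device label with 7.1.4, so that it covers events related to use of the device, including poor instructions, malfunction, use error and misuse.
2. Define the procedure label as a causal relationship to the procedure, whenever the event begins.
3. State that both labels may apply to one event.
4. Check that the adverse event form lets both relationships be recorded.

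The cost is a few sentences and one form check. Coincidental events during the procedure would lose the procedure label, and late procedural complications and indirect device effects would gain the label that fits them. Design, endpoints, sample size and patient care do not change.
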